4.4 Safety Objectives

Safety of the procedure will be assessed by the number of SADRs and SUSARs within the 2 year time-frame of the trial related to the implants. Reoperations due to new accidents or incidents at other sites than the operated site will be recorded, but not counted as related to the implant.

Document:	Clinical Study Protocol
Version:	V07
Page number:	48 of 80
Acronym	Nose to Knee II

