availability of material. In case of some diseases harvesting of healthy cartilage might not even be possible. Furthermore, it has been shown that properties of articular chondrocytes are dependent on age, while those of nasal chondrocytes are less age dependent and show greater proliferation and differentiation capacity. This might allow this technique to be applied to older patients or those with insufficient amounts of healthy articular cartilage.

Overall the risk for the patient is not considered to be higher as compared to standard procedures, but the benefits might have a significant impact especially for large defects.

Expected Adverse Reactions

Based on the experience of the phase I study, no major risks are expected. Expected adverse reactions are mostly related to the tissue withdrawal and implantation:

Expected Adverse Reaction related to nose cartilage withdrawal

		hematoma
ш	LUCAI	Helliatollia

- Local bleeding
- Local pain

Expected Adverse Reaction related to tissue implantation

Local:

- Pain
- Swelling and/or hematoma
- Plate removal in case of necessary osteotomy

Systemic:

- Post-anesthetic nausea
- vomiting
- fever

No adverse reactions are expected to follow-up procedures such as MRI/dGEMRIC. These expected adverse reactions are common for the standard treatment and therefore will only be classified according to chapter 10.1.1 and recorded in the CRF. They are not subject to reporting.

Risk assessment

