5.4 Safety Outcomes

The study will evaluate the safety of the implantation of an immature or a mature graft by the number of SADRs or SUSARs from baseline assessment up to 60-months follow-up assessment.

Adverse events/adverse drug reaction will be graded according to severity, expectedness, and relationship to trial treatment and reported according to the regulations.

No adverse events are expected except for those associated with any operation (see chapter 3.7)

Document:	Clinical Study Protocol
Version:	V07
Page number:	49 of 80
Acronym	Nose to Knee II

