9.2.5 Assessment of safety outcomes

9.2.5.1 Adverse events

All AEs (see Chapter 10 for definition) will be recorded in the eCRF. Among the expected adverse events are those associated with the application of the IMP (anesthesia & operation) as described in Chapter 3.7 under "Risks & Benefits". Other adverse events can be associated with surgical and medical procedures, arthralgia, joint effusion, decreased joint range of motion, and infections (joint, wound) or related to the IMP itself. These parameters will be checked at each follow-up visit or if the patient reports any kind of indisposition in between the visits.

All SAEs will be reported to the Sponsor-investigator or his designee according to the SOP of the Sponsor. Information in the reporting form includes: reporting center, Patient-ID, Information on surgery, other treatments already performed and details of the adverse event (affected site, symptoms, time of onset/end, time course, diagnosis and expected outcome (if possible)). The PI of the respective clinic as well as the Sponsor-investigator or his designee will perform an assessment on causality and decide on the necessary reporting.

All SAEs resulting in death will be reported to the ethical committee and the national competent authority as well as to Swissmedic within 7 days.

Document:	Clinical Study Protocol
Version:	V07
Page number:	58 of 80
Acronym	Nose to Knee II

All SUSARs and SADRs will be reported by the Sponsor-Investigator to Swissmedic, the respective national competent authorities and the local ethical committee within 7 days in case of death; otherwise within 15 days, as well as to all investigators involved in the trial. Reports to local ethical committees will be performed by the PI of the respective site.

Any occurring adverse event will be documented and treated during and after the trial. The patients will be followed until side effects are resolved or stable for at least 3 months.

9.2.5.2 Laboratory parameters

Not applicable

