10.1.1 Definition and assessment of (serious) adverse events and other safety related events

An Adverse Event (AE) is any untoward medical occurrence in a patient or a clinical investigation participant administered a pharmaceutical product and which does not necessarily have a causal relationship with the study procedure. An AE can therefore be any unfavorable and unintended sign (including an abnormal laboratory finding), symptom, or disease temporally associated with the use of a medicinal (investigational) product, whether or not related to the medicinal (investigational) product.

A Serious Adverse Event (SAE) is classified as any untoward medical occurrence that:

- results in death.
- is life-threatening,
- requires in-patient hospitalization or prolongation of existing hospitalization.
- · results in persistent or significant disability/incapacity, or
- · is a congenital anomaly/birth defect.

In addition, important medical events that may not be immediately life-threatening or result in death, or require hospitalization, but may jeopardize the patient or may require intervention to prevent one of the other outcomes listed above should also usually be considered serious. [ICH E2A]

Examples of such events are intensive treatment in an emergency room or at home for allergic bronchospasm, blood dyscrasia or convulsions that do not result in hospitalization, or development of drug dependency or drug abuse.

SAEs should be followed until resolution or stabilization. Participants with ongoing SAEs at study termination (including safety visit) will be further followed up until recovery or until stabilization of the disease after termination.

Assessment of Causality

Both Investigator and Sponsor-investigator make a causality assessment of the event in relation to the IMP. The causality is based on the question, whether there is a "reasonable possibility" or "no reasonable possibility" that the study treatment caused the event.

Unexpected Adverse Drug Reaction

An "unexpected" adverse drug reaction is an adverse reaction, the nature or severity of which is not consistent with the applicable product information (e.g. Investigator's Brochure for drugs that are not yet approved and Product Information for approved drugs, respectively).

Suspected Unexpected Serious Adverse Reactions (SUSARs)

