10.1.2 Reporting of serious adverse events (SAE) and other safety related events

Reporting of SAEs

All SAEs must be reported immediately and within a maximum of 24 hours to the Sponsor-Investigator of the study or his substitute. The Sponsor-Investigator will re-evaluate the SAE.

SAEs resulting in death are reported to the local Ethics Committee (via local Investigator) within 7 days.

The other Ethics Committees involved in the trial as well as Swissmedic receive SAEs resulting in death via Sponsor-Investigator within 7 days.

Reporting of SUSARs

A SUSAR needs to be reported to the local Ethics Committee (local event via local Investigator) and to Swissmedic for category B and C studies (via Sponsor-Investigator) within 7 days, if the event is fatal, or within 15 days (all other events).

The Sponsor-Investigator must inform all Investigators participating in the clinical study of the occurrence of a SUSAR. All Ethics Committees involved in the trial will be informed about SUSARs in Switzerland via Sponsor-Investigator according to the same timelines.

All SAEs having a suspected link to the IMP administered (Serious adverse drug reaction (SADR)) must be reported in the same way as SUSARs.

Reporting of Safety Signals

All suspected new risks and relevant new aspects of known adverse reactions that require safety-related measures, i.e. so called safety signals, must be reported to the Sponsor-Investigator within 24 hours. The Sponsor-Investigator must report the safety signals within 7 days to the local Ethics Committee (local event via local Investigator) and to Swissmedic in case of a category B or C study.

The Sponsor-Investigator must immediately inform all participating Investigators about all safety signals. The other Ethics Committees involved in the trial will be informed about safety signals via the Sponsor-Investigator.

Reporting and Handling of Pregnancies

Pregnant participants will be followed-up in the normal way, but will not be subjected to the dGEMRIC MRI due to the need to apply a contrast agent (Dotarem®). Further follow-up after the end of the study and the outcome of the pregnancy is not necessary.

Periodic reporting of safety

A development safety update report (DSUR) is submitted once a year to the local Ethics Committees and to the national authorities via Sponsor-Investigator.

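### The stated safety outcome counts only serious events linked to the graft, although the objective is the safety of the whole procedure

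*Protocol*

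**What the plan says.** Protocol 4.4 names the safety of the procedure as the objective: "Safety of the procedure will be assessed by the number of SADRs and SUSARs". With the qualifier that ends the sentence, safety is "assessed by the number of SADRs and SUSARs within the 2 year time-frame of the trial related to the implants". Reoperations for new accidents, or for incidents away from the operated site, are recorded but not counted as implant-related.

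Protocol 5.4 states: "The study will evaluate the safety of the implantation of an immature or a mature graft by the number of SADRs or SUSARs". Its window runs to 60 months.

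Protocol 10.1.1 has the investigator and the sponsor-investigator each "make a causality assessment of the event in relation to the" IMP, and it classes an event as a SUSAR if it is serious, unexpected and related to the product. Section 10.1.2 defines the SADR: "All SAEs having a suspected link to the IMP administered (Serious adverse drug reaction (SADR)) must be reported in the same way as SUSARs".

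On where harm should arise, Protocol 3.7 says: "Expected adverse reactions are mostly related to the tissue withdrawal and implantation". Section 9.2.5.1 adds: "Other adverse events can be associated with surgical and medical procedures", and contrasts such events with those related to the IMP itself.

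On analysis, Protocol 11.4.5 foresees the annual safety report, which summarises all SAEs, and no other safety analysis. SAP 6.1 records any AE and SAE with its relationship to the IMP. SAP 6.5 lists safety parameters by treatment actually received and compares frequencies between groups if many adverse events are observed.

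**The concern.** The intervention has three parts that can harm a patient: a nasal cartilage biopsy, an open knee operation under anaesthesia, and the graft. The objective covers all three. The counted outcome covers only what someone attributes to the third.

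Two things are at stake. First, the protocol makes claims about the procedure: negligible donor-site morbidity, and no expected risk beyond standard treatment (3.7). A count limited to graft-related events cannot support or contradict either claim. Second, whether a serious event counts depends on separating graft from surgery. Surgeons and patients know the arm (6.1, 6.2.2), the judgement is made by the investigator and the sponsor-investigator, and there is no data safety monitoring committee (1.6). Table 3.1.1 expects the mature graft to be easier to implant and fix, so operative events could be attributed differently in the two arms. The documents do not show in which direction, or whether this would happen.

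**Working it through.** No arithmetic applies: the plan states no figure for safety, and the point does not depend on sample size or power. The check sets the passages side by side.

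1. **Objective against measure.** Protocol 4.4 begins with the procedure and ends, in the same sentence, with events related to the implants. Section 5.4 speaks of implantation and counts the same categories. The measure is narrower than the objective in 4.4, and narrower than implantation if that includes the operation.

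2. **What qualifies.** A SADR is an SAE with a suspected link to the IMP. A SUSAR is serious, related to the product and unexpected, so every SUSAR is also a SADR. The count therefore reduces to SAEs linked to the IMP. Section 10.1.1 gives no separate causality category for biopsy, anaesthesia or surgery.

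3. **What falls outside.** Take a serious wound or donor-site complication that both assessors judge unrelated to the graft. Under 10.1.1 it is an SAE. Under 10.1.2 it is not a SADR. It does not enter the outcome of 4.4 or 5.4.

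4. **How firm the boundary is.** It is not firm. Section 3.7 calls the effects of biopsy and implantation adverse reactions. Section 9.2.5.1 first describes anaesthesia and operation as part of applying the IMP, then separates surgical events from those of the IMP itself. Section 10.1.1 asks about the IMP in one sentence and about the study treatment in the next. Two sites could code the same operative event differently, and both could cite the protocol.

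5. **Where the event still appears.** All AEs and SAEs are collected from consent (9.2.5.1, 10.1). Donor-site consequences are asked about from the 6-week visit onward (9.3.5 to 9.3.7). The annual report summarises all SAEs (11.4.5). Revision surgery is analysed whatever its cause (9.2.4). SAP 6.5 lists safety events by treatment received.

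6. **What those places leave open.** None sets out a table of procedure-related serious events. Revision surgery misses donor-site harm and complications that need no reoperation. The between-arm comparison in SAP 6.5 has no threshold. A listing by treatment received has no clear place for a patient who was randomised and biopsied but not implanted. SAP 4.3 says that patients excluded at surgery are not followed up, and SAP 7.1 reports two randomised patients who received no treatment.

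7. **Window.** Section 4.4 counts within 2 years. Section 5.4 counts to the 60-month assessment ("number of SADRs or SUSARs from baseline assessment up to 60-months follow-up assessment"). Follow-up after 24 months is voluntary and based on questionnaires (Synopsis, 6.1), so the two windows would rest on different sets of patients.

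**The case against.** The strongest reply is that nothing is lost. Serious procedural harm is an SAE whatever its cause, it is collected and reported, and the SAP already goes beyond SADRs and SUSARs. SAP 4.1 promises that all recorded variables will be presented by treatment group, with frequencies for categorical variables. On its face that could give SAE counts by arm. This stands in large part, and it limits the point to the stated outcome and its analysis. It does not settle it: SAP 6.5, the specific section, provides a listing and a conditional comparison, and neither section says whether patients or events are counted.

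A second reply is that a focus on the graft is defensible, since both arms have the same type of biopsy and surgical approach and differ in graft maturity. That is a fair reason to choose an IMP-related outcome, but the objective should then say so.

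A third is that much operative harm might be coded as a SADR after all. The causality test is only a reasonable possibility, infection through the transplant is a listed risk (Table 3.7.1), and the reoperation sentence in 4.4 suggests that events at the operated site may count. This also stands. It means that the exclusion depends on coding, and it does not make the count well defined.

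A reader might go further and infer that procedural harm is not an event in this trial, or is hidden. The documents do not support that, for the reasons in step 5 of the working. A reader might also infer from 3.7 that the outcome leaves out the most likely harms because of attribution. The reactions listed there are mostly non-serious (pain, swelling, haematoma, nausea, fever), so most would fall outside any count of serious events.

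**Conclusion.** The point holds in a limited form. Serious harm from the biopsy, anaesthesia or operation that is judged unrelated to the graft is collected but not counted in the outcome that Protocol 4.4 and 5.4 attach to the safety objective. The count rests on an unblinded attribution with an unclear boundary, and the SAP's wider listing leads to a between-arm comparison only under an undefined condition.

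No size can be given. The shortfall is the number of patients with an SAE minus the number with an SAE linked to the IMP, and the readable text gives neither. Invented event counts would add nothing.

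The conclusion assumes that some serious procedural events are coded as unrelated to the IMP, which 9.2.5.1 and 10.1.1 allow but do not require. It does not affect the primary analysis, and it makes no statement that either graft is unsafe. It is a cheap and worthwhile correction to how safety is summarised.

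**What to change.** In Protocol 4.4, 5.4 and 11.4.5 and in SAP 6.1 and 6.5:

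- Define the safety outcome as the number and percentage of patients with at least one SAE, by arm and whatever the attribution, with a risk difference and 95% CI.
- Use all randomised patients, including those biopsied but not implanted, shown under their randomised arm. SAP 4.4 already defines the safety population as the FAS, and SAP 4.3 rules out cross-over, so arm as randomised and as treated should agree for implanted patients. State how long the patients who were not implanted were observed.
- Show SADRs/SUSARs as a subset. Where existing SAE records allow, also show events related to biopsy, to surgery or anaesthesia, and to the graft. This breakdown is optional, because the same unblinded people would judge it.
- Let this table replace the comparison that depends on many events being seen.
- Reconcile the 2-year and 60-month windows.

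SAP section 7 already describes outcome data, so the change should be entered there as a dated addition and labelled as such. Expedited-reporting rules stay as they are.

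The cost is one extra table from data already collected, plus optional coding from SAE records, which hold surgery information and affected site (9.2.5.1). The downsides are that the reported safety rate may look less favourable, and that an all-cause count will include some events unrelated to the trial. Counting whatever the attribution takes the graft-versus-surgery judgement out of the main comparison, but it cannot remove the effect of open-label reporting.

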5. STUDY OUTCOMES

5.1 Primary Outcome

The KOOS score will be used to measure the primary outcome. The primary endpoint is the difference in the KOOS at 24 months between the two techniques (comparison of the efficacy of the technique). The KOOS score, covering the fields of Symptoms, Pain, Activities of daily life, Sport activities and Quality of life, is suitable for assessing the improvement for the patient. This validated questionnaire is widely used to assess efficacy of cartilage repair therapies.

5.2 Secondary Outcomes

The stability and integration as well as the morphological properties of the graft will be assessed by the MOCART and 3D MOCART Scores (magnetic resonance observation of cartilage repair tissue) derived from the MRI. The secondary endpoint will be the 24-month assessment. MRI will be performed at 3, 12, 24 months follow-up.

The remodeling of the tissue after implantation towards native cartilage will be assessed by dGEMRIC evaluation (MRI) from the 24-month assessment of the relative \Box R1. The dGEMRIC evaluation will be recorded at 3, 12, 24 months follow-up.

The KOOS will be recorded for patients at baseline visit 1 or 2 and at the 12- and 24-month follow-up assessments. Variations over time will be recorded through completion of the questionnaires at enrolment and at each follow-up visit (12 and 24 months after treatment). An increase of at least 10 points after 2 years in the KOOS is considered a relevant improvement for the patient, thus proving the efficacy of the treatment.

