3.6 Explanation for choice of comparator (or placebo)

As the most promising approach currently, and reported to provide clinical improvement to young patients with focal cartilage defects in mid-term follow-up (Kon et al, 2009), we have selected cell-therapy techniques as the most appropriate comparator. The established cell-based technique MACI® has been used in clinical applications since 1998 and is a standard product with marketing authorization in Europe since 2013 (currently suspended). In order to eliminate differences due to the cell source and allow a more appropriate evaluation of the impact of graft maturation on the clinical outcome, nasal chondrocytes instead of articular chondrocytes will be used (figure. 3.6.1), therefore exploiting the concept of cellular therapies, not using a licensed product. Since nasal chondrocytes have been proven *in vitro* to have superior properties as compared to articular chondrocytes, results at least comparable to the standard MACI® procedure can be expected.

[figure not shown]

Fig. 3.6.1 Illustration of the procedures to generate the NC-based IMPs and of their main characteristics

Document:	Clinical Study Protocol
Version:	V07
Page number:	42 of 80
Acronym	Nose to Knee II

We believe that in this setting, where a mature and immature graft is manufactured in a similar way using nasal chondrocytes, the superiority of the mature graft in comparison to the immature graft can be shown.

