4. STUDY OBJECTIVES

4.1 Overall Objective

The study aims at the comparison of a therapy with a mature graft versus a therapy with an immature graft for the regeneration of articular cartilage lesions in the knee after injury. Two main innovations are introduced: 1) the use of autologous nasal chondrocytes (NC) as cell source superior to articular chondrocytes (AC) and 2) the delivery of a mature graft as opposed to an immature graft. Data will also be analyzed retrospectively to identify the possibility of treatment selection in relation to the time after the initial cartilage injury (acute vs chronic cartilage lesions as defined by onset of symptoms).

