4.2 Primary Objective

This proposed phase II trial seeks to primarily define whether a mature graft will improve the clinical efficacy for the patient, leading to an increase of at least 10 points in the main primary outcome (self-assessed score KOOS) after 24 months as compared to the group receiving the immature graft. Comparison between groups will allow assessment of whether the mature graft is superior to the immature graft.

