9.2.4 Definition of treatment failure

Treatment failure is defined as: "Objective pathological clinical findings by the investigator, which are directly correlated with subjective patients complaints resulting in a deterioration of the subjective clinical outcome assessed by KOOS and the 5 KOOS subscores."

Clinical deterioration is defined as reduction in the KOOS score of > 10 compared to baseline. A non-responding to treatment is defined as improvement of < 10 in the KOOS score.

Furthermore, revision surgery rate independent of cause and deterioration of the subjective clinical outcome assessed by KOOS and the 5 KOOS subscores independent of correlation with IMPs will be assessed and analyzed.

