11.2 Determination of Sample Size

Sample size was estimated to be such that it would be able to show the superiority of N-TEC to N-CAM regarding the primary endpoint. Assumptions for sample size calculation were based on a study (Saris et al., 2008), in which an increase in a mean overall KOOS score after 18 months of 18 points to a final value of 74.73 with a standard deviation of 17.01 was reported. We have assumed that the effect size after 24 months will be at least as big.

Sample size was calculated using a resampling method. Each sample size ($n_i=1,...,21=40,...,160$) was evaluated by sampling R = 999 times, $n_i/2$ KOOS scores from a normal distribution with $\square=75$ and $\square=17$ for the N-CAM group, and $n_i/2$ KOOS scores from a normal distribution with $\square=75+\square$ and $\square=17$ for the N-TEC group. The size of \square was varied between 5 and 15. Values that exceeded 100 were set to 100.

N-CAM and N-TEC were tested for a difference in KOOS score using a two-sided t-test. Superiority of N-TEC to N-CAM was declared when the test showed a significant result. Sample size was set to ensure at least 80 % power (1 - \square = 0.8), at a significance level of \square = 5 %.

For this study, 108 patients should be recruited to ensure 97 evaluable patients at a power of 80%, considering an overall drop-out rate of 10% (Figure 11.2.1).

[figure not shown]

Fig. 11.2.1: Sensitivity of the sample size with regard to absolute difference in KOOS after 24 months (N-TEC vs. N-CAM), assuming a mean KOOS of 75 for N-CAM. An example is given based on an expected absolute difference of 10 score points (Curves are smoothed and are for illustrative purpose only)

Document:	Clinical Study Protocol
Version:	V07
Page number:	63 of 80
Acronym	Nose to Knee II

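### Protocol 5.2 calls a 10-point KOOS rise proof of efficacy, but a before-after rise cannot prove the efficacy of either graft when both arms receive nasal-chondrocyte grafts and no standard or untreated arm exists

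*Protocol*

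**What the plan says.** Protocol 5.2 lists KOOS at baseline, 12 and 24 months and adds: "Variations over time will be recorded through completion of the questionnaires at enrolment and at each follow-up visit". The next sentence says that a KOOS increase of at least 10 points after 2 years "is considered a relevant improvement for the patient, thus proving the efficacy of the treatment".

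The figure of 10 points has two uses in the protocol:

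- **Within a patient.** Protocol 9.2.4 (and 4.3) says: "A non-responding to treatment is defined as improvement of < 10 in the KOOS score". The rule in 5.2, at least 10, is the exact complement.
- **Between arms.** Protocol 4.2 looks for a 10-point advantage of the mature graft "after 24 months as compared to the group receiving the immature graft", and 11.1 calls a between-arm difference of 10 or more clinically relevant.

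On the comparator, Protocol 3.6 describes a setting "where a mature and immature graft is manufactured in a similar way using nasal chondrocytes", and says the control arm is "therefore exploiting the concept of cellular therapies, not using a licensed product". No arm receives a licensed product, standard care, sham or no graft.

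**The concern.** Only the between-arm use of the 10 points has a randomised control. A rise from baseline in either arm mixes any effect of the graft with several other things:

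- debridement at implantation (Synopsis, Study design);
- the rehabilitation programme (Protocol 8.7);
- ligament, alignment or bone-graft surgery, which the eligibility criteria permit (Protocol 7.1);
- expectation, because KOOS is self-rated (9.2.1) and patients know their graft (6.2.2);
- regression to the mean, because entry requires KOOS of 75 or less (7.1).

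The trial has nothing against which to subtract these. What is at stake is the conclusion the protocol allows. Read literally, 5.2 would let a 10-point rise count as proven efficacy for both products even if the randomised comparison found no difference between them.

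**Working it through.** **1. Reproduce the plan's own figure.** Inputs from Protocol 11.2: N-CAM mean 75, N-TEC mean 85, SD 17, values above 100 set to 100, two-sided t-test at 5%. Simulating this (40,000 runs, 48 + 49 = 97 patients) gives 80.2% power, and 97 / 0.9 = 107.8, rounded up to 108. The stated 97 and 108 reproduce. They concern the between-arm test only.

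**2. Rise from baseline implied by the same inputs.** Protocol 11.2 cites "an increase in a mean overall KOOS score after 18 months of 18 points to a final value of 74.73" and assumes an effect at least as large at 24 months.

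- Implied baseline: 74.73 − 18 = 56.73, about 57.
- N-CAM rise: 75 − 56.73 = 18.3 (17.7 after the cap at 100).
- N-TEC rise, if the 10-point advantage is real: 85 − 56.73 = 28.3 (26.5 after the cap).

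**3. Share of patients reaching 10 points.** This takes the rule per patient, as its wording and 9.2.4 suggest. Assumptions not in the documents: SD 17 also at baseline, a baseline-to-outcome correlation ρ of 0.3, 0.5 or 0.7, and normally distributed change.

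SD of change = 17 × √(2(1 − ρ)) = 20.1, 17.0 and 13.2.

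Share = Φ((mean rise − 10) / SD of change).

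- Identical grafts, rise 18 in both arms: Φ(8/20.1), Φ(8/17.0), Φ(8/13.2) = 65%, 68%, 73% in each arm.
- N-TEC with a true 10-point advantage, rise 28: Φ(18/20.1), Φ(18/17.0), Φ(18/13.2) = 81%, 86%, 91%.

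The cap does not change who reaches 10 points: a patient who enters at 75 or less and is capped at 100 has risen by at least 25.

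**4. Dependence on the baseline.** The documents give no expected baseline mean for this trial. Holding N-CAM at 75 and varying the assumed baseline:

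| Mean baseline | N-CAM rise | Share, ρ = 0.3 | ρ = 0.5 | ρ = 0.7 |
|---|---|---|---|---|
| 50 | 25 | 77% | 81% | 87% |
| 57 | 18 | 65% | 68% | 73% |
| 60 | 15 | 60% | 62% | 65% |
| 65 | 10 | 50% | 50% | 50% |
| 70 | 5 | 40% | 38% | 35% |

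N-CAM's expected mean rise falls to 10 at a baseline of 65 (64.5 with the cap).

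**5. Regression to the mean, for scale only.** Suppose scores in the source population are normal with mean m and SD 17, and patients enter at 75 or less. With a = (75 − m)/17, the mean at entry is m − 17 φ(a)/Φ(a), and the expected drift back is (1 − r) × (m − entry mean), where r is the test-retest correlation.

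- m = 57: entry mean 52.5. With r = 0.7, drift is 0.3 × 4.5 = 1.4 points.
- m = 70: entry mean 59.5. With r = 0.3, drift is 0.7 × 10.5 = 7.4 points.

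Over these assumed values, 1.4 to 7.4 points of a rise could appear with no treatment effect. The documents do not allow the other components to be sized.

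**The case against.** **The clause drives no analysis.** This is the strongest reply, and it stands. Protocol 11.1 ties the primary objective to the between-arm hypotheses. The models in Protocol 11.4.2 and 11.4.3 and SAP 6.3 are between-arm, SAP 2.4 frames every endpoint as superiority of N-TEC over N-CAM, and the SAP does not repeat the sentence. It is still the place where the outcomes section says what would prove efficacy, and the Synopsis names evaluating efficacy as an aim alongside comparing maturation stages.

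**The words for change from baseline are missing from the sentence.** True, and 4.2 speaks of a 10-point increase when it means the difference between arms. The reading is inferred from the preceding sentence about change over time and from the matching non-response definition. It is the better reading but not explicit.

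**A reader might infer an arm-level success rule that both arms would be almost certain to pass.** The documents do not support this. They set no rule for an arm's mean rise and no within-arm test against 10 points. The sentence speaks of improvement for the patient, and at patient level the rule is met by a majority on the planning values, not by nearly everyone. Even that figure leans on another study's baseline.

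**A reader might also infer from Protocol 4.1 that the trial claims to test nasal against articular chondrocytes.** It does not. Section 4.1 says the innovation is introduced, and 3.6 states openly that using nasal cells in both arms removes cell source from the comparison. No change to 4.1 is needed on this ground.

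**The open-label limitation is already disclosed** in Protocol 6.1. That is fair, but the disclosure does not make an uncontrolled rise into proof.

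**Conclusion.** The point holds as a correction to one inference in Protocol 5.2. A rise of 10 points from baseline may serve as a threshold of relevant improvement for a patient, but it cannot prove the efficacy of N-TEC or N-CAM. The randomised comparison can show the effect of graft maturation, not the effect of either graft against standard care or no graft.

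On the planning values, about 65% to 73% of patients per arm would meet the threshold with identical grafts. This rests on a baseline of about 57 taken from the external study, SD 17 at both times and an assumed correlation of 0.3 to 0.7; at a baseline of 65 the share is 50%. The invalidity of the inference does not depend on these figures, because it follows from the absence of a control for the within-arm change.

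The documents do not show that anyone planned to report a null primary result as proven efficacy. The wording leaves room for it and should not.

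**What to change.** In Protocol 5.2, delete the clause after the comma in "is considered a relevant improvement for the patient, thus proving the efficacy of the treatment". Keep 10 points as a descriptive per-patient improvement threshold, say explicitly that it is measured from baseline, and report the share reaching it by arm. Add one sentence: efficacy conclusions rest only on the between-arm comparison of N-TEC with N-CAM.

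A between-arm comparison of the share improving by at least 10 points is not among the analyses listed in Protocol 11.4.3 or SAP 6.3. If it is added, label it supplementary. The SAP is dated 28 November 2022, and its section 7.3 describes the observed outcome distribution, so label it post hoc as well if it is added after outcome data were seen. If the protocol can no longer be amended, put the clarification in the final statistical report.

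The cost is wording, plus a simple tabulation from KOOS data already collected. The sponsor gives up an uncontrolled efficacy claim; hypotheses, models and sample size stay as they are.
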